### **25c Analyses of secondary outcomes**

Mechanistic, clinical and safety outcomes will be compared between the treatment groups using binary logistic regression, Cox proportional hazards regression (death), ordinal logistic regression (mRS) or multiple linear regression (BI, TICS, t-MMSE, ZDS, EQ-5D, EQ-VAS, as appropriate (**Table A**), in exploratory analyses.

**25d Covariate adjustment:** Analyses will be adjusted for minimisation covariates including age, stroke severity (NIHSS), time after stroke, systolic blood pressure, and received reperfusion therapy.

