### **9 Sample size/power considerations**

ENOS-2 is a feasibility study hence there is no formal sample size calculation. However, recruitment of 100 participants would allow an adjusted common odds ratio, acOR 0.51 to be detected, assuming mRS distribution as in; alpha 0.05, power 0.80. The number of targeted participants will be 100 with ischaemic stroke (50 randomised to GTN, 50 randomised to sham) and 20 with intracerebral haemorrhage for safety (10 randomised to GTN, 10 randomised to sham).

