### **11 Randomisation**

Patients will be randomised 1:1 to receive either 5 mg transdermal GTN versus sham transdermal DuoDERM hydrocolloid dressing placed on the back or shoulders for two days. Randomisation will be performed by the Stroke Trials Unit (STU) in Nottingham and involve computerised stratification by stroke type (IS or not known; ICH) and minimisation on age, severity, time, systolic blood pressure and candidate for or received reperfusion therapy. Patients, relatives, researchers, and outcome assessors will be masked to treatment allocation.

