### **25b Analyses of Primary endpoint**

Recruitment, treatment and follow-up rates will be estimated using tabulation and graphical presentation.

It is likely that a large definitive trial would be feasible if at least 70 participants were recruited into this study, that compliance with randomised treatment was high and that a high proportion of follow-up data was available.

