**Table 4. Clinical Outcomes at Day 2.**

Data are number (%), median [IQR], or mean (standard deviation).

Variable	Statistic	N	All	GTN	Sham	aOR/aMD (95%CI)	Difference (p)
Patients randomised	N	xxx	xxx	xxx	xxx		
Mechanistic Outcomes							
Blood Pressure							
SBP (mmHg)	Mean (SD)	xxx	xxx (xxx)	xxx (xxx)	xxx (xxx)	xxx (xxx, xxx)	MLR
DBP (mmHg)	Mean (SD)	xxx	xxx (xxx)	xxx (xxx)	xxx (xxx)	xxx (xxx, xxx)	MLR
Heart rate (bpm)	Mean (SD)	xxx	xxx (xxx)	xxx (xxx)	xxx (xxx)	xxx (xxx, xxx)	MLR
Clinical Outcomes							
Impairment							
NIHSS (/100)	Mean (SD)	xxx	xxx (xxx)	xxx (xxx)	xxx (xxx)	xxx (xxx, xxx)	MLR
Neurological deterioration NIHSS change from baseline (point increase)							
NIHSS ≥ 4	Mean (SD)	xxx	xxx (xxx)	xxx (xxx)	xxx (xxx)	xxx (xxx, xxx)	MLR
NIHSS ≥ 2	Mean (SD)	xxx	xxx (xxx)	xxx (xxx)	xxx (xxx)	xxx (xxx, xxx)	MLR
Hand weakness						xxx (xxx, xxx)	OLR
...Normal strength	n (%)	xxx	xxx (xxx)	xxx (xxx)	xxx (xxx)		
...Reduced strength	n (%)	xxx	xxx (xxx)	xxx (xxx)	xxx (xxx)		
...Some movement	n (%)	xxx	xxx (xxx)	xxx (xxx)	xxx (xxx)		
...Paralysis	n (%)	xxx	xxx (xxx)	xxx (xxx)	xxx (xxx)		
Feeding ability						xxx (xxx, xxx)	OLR
...Normal diet	n (%)	xxx	xxx (xxx)	xxx (xxx)	xxx (xxx)		
...Soft diet	n (%)	xxx	xxx (xxx)	xxx (xxx)	xxx (xxx)		
...NG feed	n (%)	xxx	xxx (xxx)	xxx (xxx)	xxx (xxx)		
...PEG feed	n (%)	xxx	xxx (xxx)	xxx (xxx)	xxx (xxx)		
...IV/SC fluids	n (%)	xxx	xxx (xxx)	xxx (xxx)	xxx (xxx)		
...Nothing	n (%)	xxx	xxx (xxx)	xxx (xxx)	xxx (xxx)		
Dysphagia, DSRS (/12)	Mean (SD)	xxx	xxx (xxx)	xxx (xxx)	xxx (xxx)	xxx (xxx, xxx)	MLR
Events up to day 2							
Death	n (%)	xxx	xxx (xxx)	xxx (xxx)	xxx (xxx)	xxx (xxx, xxx)	BLR
Symptomatic ICH	n (%)	xxx	xxx (xxx)	xxx (xxx)	xxx (xxx)	xxx (xxx, xxx)	BLR
ICH expansion	n (%)	xxx	xxx (xxx)	xxx (xxx)	xxx (xxx)	xxx (xxx, xxx)	BLR
Symptomatic Recurrent Stroke						xxx (xxx, xxx)	OLR

Variable	Statistic	N	All	GTN	Sham	aOR/aMD (95%CI)	Difference (p)
...IS	n (%)	xxx	xxx (xxx)	xxx (xxx)	xxx (xxx)		
...haemorrhagic	n (%)	xxx	xxx (xxx)	xxx (xxx)	xxx (xxx)		
...unknown type	n (%)	xxx	xxx (xxx)	xxx (xxx)	xxx (xxx)		
...none	n (%)	xxx	xxx (xxx)	xxx (xxx)	xxx (xxx)		
Clinical neuro-deterioration	n (%)	xxx	xxx (xxx)	xxx (xxx)	xxx (xxx)	xxx (xxx, xxx)	BLR
MEB	n (%)	xxx	xxx (xxx)	xxx (xxx)	xxx (xxx)	xxx (xxx, xxx)	BLR
Acute coronary Syndrome (ACS)	n (%)	xxx	xxx (xxx)	xxx (xxx)	xxx (xxx)	xxx (xxx, xxx)	BLR
...STEMI							
...NSTEMI							
...Unstable angina							
...None							

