**Table 9. Participants with at least one serious adverse event by organ randomised to GTN versus Sham control.**

Data are number (%), and comparison by binary logistic regression.

	All			Fatal		
	GTN	Control	Difference (p)	GTN	Control	Difference (p)
Number						
Cardiovascular	xxx (xxx)	xxx (xxx)	xxx (xxx, xxx), p=0.xxx	xxx (xxx)	xxx (xxx)	xxx (xxx, xxx), p=0.xxx
Hypotension	xxx (xxx)	xxx (xxx)	xxx (xxx, xxx), p=0.xxx	xxx (xxx)	xxx (xxx)	xxx (xxx, xxx), p=0.xxx
Nervous system	xxx (xxx)	xxx (xxx)	xxx (xxx, xxx), p=0.xxx	xxx (xxx)	xxx (xxx)	xxx (xxx, xxx), p=0.xxx
Haemorrhagic transformation	xxx (xxx)	xxx (xxx)	xxx (xxx, xxx), p=0.xxx	xxx (xxx)	xxx (xxx)	xxx (xxx, xxx), p=0.xxx
Transient ischaemic attack	xxx (xxx)	xxx (xxx)	xxx (xxx, xxx), p=0.xxx	xxx (xxx)	xxx (xxx)	xxx (xxx, xxx), p=0.xxx
Respiratory	xxx (xxx)	xxx (xxx)	xxx (xxx, xxx), p=0.xxx	xxx (xxx)	xxx (xxx)	xxx (xxx, xxx), p=0.xxx
Gastrointestinal	xxx (xxx)	xxx (xxx)	xxx (xxx, xxx), p=0.xxx	xxx (xxx)	xxx (xxx)	xxx (xxx, xxx), p=0.xxx
Genitourinary	xxx (xxx)	xxx (xxx)	xxx (xxx, xxx), p=0.xxx	xxx (xxx)	xxx (xxx)	xxx (xxx, xxx), p=0.xxx
Haematological/immunological	xxx (xxx)	xxx (xxx)	xxx (xxx, xxx), p=0.xxx	xxx (xxx)	xxx (xxx)	xxx (xxx, xxx), p=0.xxx
Metabolic/endocrine	xxx (xxx)	xxx (xxx)	xxx (xxx, xxx), p=0.xxx	xxx (xxx)	xxx (xxx)	xxx (xxx, xxx), p=0.xxx
Musculoskeletal/cutaneous	xxx (xxx)	xxx (xxx)	xxx (xxx, xxx), p=0.xxx	xxx (xxx)	xxx (xxx)	xxx (xxx, xxx), p=0.xxx
Miscellaneous	xxx (xxx)	xxx (xxx)	xxx (xxx, xxx), p=0.xxx	xxx (xxx)	xxx (xxx)	xxx (xxx, xxx), p=0.xxx
Other	xxx (xxx)	xxx (xxx)	xxx (xxx, xxx), p=0.xxx	xxx (xxx)	xxx (xxx)	xxx (xxx, xxx), p=0.xxx
Total	xxx (xxx)	xxx (xxx)	xxx (xxx, xxx), p=0.xxx	xxx (xxx)	xxx (xxx)	xxx (xxx, xxx), p=0.xxx

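### Rare day-2 and SAE comparisons are assigned ordinary logistic regression, six-term in Table 4, with no rule for sparse or empty cells

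*SAP*

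**What the plan says.** SAP 25c assigns binary logistic regression to binary mechanistic, clinical and safety outcomes, and names "Cox proportional hazards regression (death" for mortality. The adjustment rule in 25d reads: "Analyses will be adjusted for minimisation covariates including age, stroke severity (NIHSS), time after stroke, systolic blood pressure, and received reperfusion therapy". With treatment, that makes six model terms, and no exception is given for outcomes with few events.

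Table 4 heads its effect column as an adjusted odds ratio or mean difference. It assigns logistic regression to day-2 death, "Symptomatic ICH", ICH expansion, major extracranial bleeding, acute coronary syndrome and pulmonary embolism, and to headache, hypotension and hypertension.

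Table 9 covers participants with an SAE by organ class, for all SAEs and for fatal ones: "Data are number (%), and comparison by binary logistic regression". It does not say whether that regression is adjusted. Fisher's exact test is named only in the relatedness rows of Table 8, as an alternative to chi-square; the treatment-time rows of that table use logistic regression.

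On size, SAP 9 states: "The number of targeted participants will be 100 with ischaemic stroke (50 randomised to GTN, 50 randomised to sham". A second, smaller haemorrhage group of ten per arm is added to look at safety, so the total is 120, or 60 per arm. SAP 25b regards a definitive trial as likely to be "feasible if at least 70 participants were recruited into this study".

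**The concern.** A maximum-likelihood logistic model has no finite solution when the covariates, or treatment alone, split events from non-events perfectly. With a handful of events and six terms this happens often. With treatment alone it happens whenever one arm has no events. The table cell then holds an infinite or missing odds ratio, or a Wald p-value that reflects where the iterations stopped and not the data.

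Safety is part of the objective in the protocol synopsis, and the ICH patients are included for safety. All events falling in one arm is a pattern that a safety table should show clearly, and it is the pattern in which the specified estimate fails. Without a rule fixed in advance, the replacement analysis would be chosen after the data have been seen.

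**Working it through.** **The plan's own figure.** There is none to reproduce. The SAP gives no expected event count, rate or power for death, day-2 events or SAEs.

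**Inputs from the documents.** N=120 (SAP 9), 1:1 allocation (SAP 11), and 70 as the lower recruitment mark (SAP 25b; the protocol's Statistics section says 75). Six terms (SAP 25d). Day-90 death rates from SAP Table B, averaging the two arms: ENOS (12+13)/2 = 12.5%; ENOS-early (8+20)/2 = 14%; RIGHT-2 (23+19)/2 = 21%.

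**Assumptions.** Day-2 and SAE event rates of 1 to 10%. In the main simulation the log effects per SD were 0.5 for age, 0.8 for NIHSS, 0 for time and 0.1 for systolic BP, with -0.2 for reperfusion (40% treated).

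**Step 1: six-term logistic model.** Simulated trials (600 per cell), with separation detected by linear programming. Share of trials separated or with no events:

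| Event rate | N=120 | N=70 |
|---|---|---|
| 1% | 88% | 97% |
| 2% | 69% | 87% |
| 3% | 45% | 74% |
| 5% | 21% | 50% |
| 10% | 1.5% | 13% |

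A second simulation with a different covariate set-up (400 trials per cell, two prognostic covariates) gave 89, 72, 45 and 22% at N=120 and 96, 88, 77 and 52% at N=70 for rates of 1, 2, 3 and 5%.

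**Step 2: treatment-only model.** The chance that at least one arm has no events is 2q - q², where q = (1-p)^n and n is the number per arm. At p=3% and n=60, q = 0.97^60 = 0.161, so 2(0.161) - 0.026 = 0.30.

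| Event rate | 60 per arm | 35 per arm |
|---|---|---|
| 1% | 80% | 91% |
| 2% | 51% | 74% |
| 3% | 30% | 57% |
| 5% | 9% | 31% |

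Dropping the covariates therefore helps but does not solve the problem.

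**Step 3: what the reader of the table would see.** For 6/60 v 0/60, two-sided Fisher p = 2 × C(60,6)/C(120,6) = 2 × 50,063,860/3,652,745,460 = 0.027. The treatment-only logistic fit diverges. After 20 Newton steps the log odds ratio is about 19 with a standard error of about 5,189, so z is about 0.004 and the Wald p-value exceeds 0.99. Stopping sooner gives a smaller p-value, so the printed figure is arbitrary.

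**Step 4: fatal SAEs in Table 9.** Expected deaths at N=120 are 120 × 12.5% = 15.0, 120 × 14% = 16.8 and 120 × 21% = 25.2. The table has ten organ-class rows if hypotension, haemorrhagic transformation and TIA are read as sub-rows. The average is then 15.0/10 to 25.2/10, or 1.5 to 2.5 deaths per class over both arms.

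**Step 5: Cox model for death.** Those 15.0 to 25.2 deaths give 2.5 to 4.2 per term. In 2,000 simulated trials per scenario at N=120, the six-term model was non-estimable in 0 to 0.5%, with 94 to 95% coverage and an SD of the log hazard ratio of 0.46 to 0.68, against 0.41 to 0.60 unadjusted. At N=70 (8.8 to 14.7 deaths) it was non-estimable in 0.4 to 7%, with an SD of 0.69 to 1.05 against 0.57 to 0.73 unadjusted.

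**The case against.** The case on the other side has real force.

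- **Counts stay visible.** Tables 4, 8 and 9 print number and percentage by arm, so a 6 v 0 split would be seen whatever the regression returns. This stands. A reader might infer that a harm signal could vanish from the report; the table layouts do not support that. The defect lies in the estimate and p-value printed beside the counts.
- **The comparisons are exploratory.** SAP 25c says so and adds a qualifier of appropriateness; the protocol's safety section has SAEs summarised descriptively. This limits the weight of the point. The qualifier, however, names neither a trigger nor an alternative.
- **Table D already lists a chi-square test for binary data.** It does, and chi-square does not fail through separation. It is not exact, gives no interval, and is not what Tables 4 and 9 assign to these rows.
- **Adjustment in Table 9 is not stated.** Correct. It rests on reading 25d as covering harms. If Table 9 is unadjusted, the Step 2 figures apply to it, not those in Step 1.
- **Rates are assumed, and some Table 4 rows may be common.** Correct. At 10% the six-term model fails in only 1.5% of trials at N=120, so headache or hypotension may be estimable.
- **Smaller splits are not significant anyway.** For 4 v 0 of 60 per arm, Fisher gives p=0.12, so that split does not show an exact test finding what logistic regression misses. The 6 v 0 split does.

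**Conclusion.** The point holds for rare binary safety rows. In Table 4, events at about 3% or less would leave the specified adjusted odds ratio without a usable value in roughly 45 to 88% of trials at N=120 and 74 to 97% at N=70. In Table 9, the same applies if 25d governs it; if not, an arm is empty in about 30 to 80% of trials at those rates with 60 per arm. These figures rest on assumed event rates of 1 to 3% and, for the six-term model, assumed covariate effects. Two sets of covariate assumptions agree within about 3 percentage points.

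A reader might infer from the low number of deaths per term that the Cox model for death is also unsupportable. The mortality rates in Table B do not bear this out at the planned size: the model fits in at least 99.5% of simulated trials with near-nominal coverage, and most of its imprecision is shared by the unadjusted model. It becomes noticeably less stable only if recruitment ends near 70.

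The consequence is confined to how safety comparisons are reported. The feasibility endpoint is unaffected. The change should be made before database lock.

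**What to change.** In SAP 25c and 25d, with a matching footnote to Tables 4, 8 and 9, state that where either arm has no events, or total events fall below a pre-set modest count (for example about 10 in total), the comparison will be n/N by arm, an unadjusted risk difference with a score or exact 95% confidence interval, and Fisher's exact test. Any adjusted odds ratio for such a row should come from Firth-penalised logistic regression. State also whether Table 9 is adjusted.

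The trigger should be a total count. Ten events per term would mean 10 × 6 = 60 events, half of all 120 participants, and would rule out practically every adjusted logistic model, including those at a 10% rate that nearly always fit.

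The Cox model for death can stay. A treatment-only Cox model alongside it is optional and matters mainly if recruitment ends near 70.

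The cost is SAP wording only, with no change to data collection. The downside is that fully adjusted maximum-likelihood odds ratios will not be shown for rare events.

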**Table A. Characteristics of completed trials of transdermal glyceryl trinitrate.**

	GTN-1 30	GTN-2 31	GTN-3 24	RIGHT 28,32,33	ENOS 2,34-36	RIGHT-2 3,37-40
Setting	Hospital	Hospital	Hospital	Pre-hospital	Hospital	Pre-hospital
Time window (hr)	<120 hours	<72 hours	<120 hours	<4 hours	<48 hours	<4 hours
Stroke type	IS/ICH	IS/ICH	IS/ICH	IS/ICH	IS/ICH	IS/ICH
SBP range (mmHg)	No limits	100-230	140-220	>140	140-220	>120
Treatment blinding	Double-blind	Open-label	Single-blind	Single-blind	Single-blind	Single-blind
GTN dose (mg)	5	5/10	5	5	5	5
Thrombolysis given	N/A	N/A	N/A	After GTN	Before GTN	After GTN
Sample size						
Intended	38	90	18	80	>3500	850
Achieved	37	90	18	41	4011	1149

ICH: intracerebral haemorrhage; IS: ischaemic stroke; N/A: not applicable; SBP: systolic blood pressure

GTN lowered BP, increased heart rate, and did not alter cerebral blood flow (assessed using xenon CT) or platelet function. The safety and efficacy of GTN in patients with acute stroke (IS, ICH) has been assessed in two large phase III trials.

**International hospital-based MRC ENOS trial:** In comparison with no GTN, transdermal GTN was not associated with any difference in functional outcome (mRS), disability/Activities of Daily Living (BI), cognition (tMMSE, TICS, animal naming), mood (ZDS) or quality of life (EQ-5D/HUS, EQ-VAS) (Table B). No safety issues were found with GTN.

In the subgroup of patients randomised within 6 hours of ictus (average time from event to randomisation 263 minutes) (identified here as 'ENOS-early'), treatment with GTN was associated with reduced death, and improved functional outcome (mRS, BI) and quality of life (Table B)

**UK ambulance-based BHF RIGHT-2 trial:** The average time to treatment was 70 minutes. In comparison with sham, transdermal GTN was not associated with any differences in functional outcome (mRS), disability/Activities of Daily Living (BI), cognition (tMMSE, TICS, animal naming), mood (ZDS) or quality of life (EQ-5D/HUS, EQ-VAS).

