### **7b Secondary Objectives:**

- i. To identify potential proof of concept on whether GTN reduces disability, low mood, poor cognition, and low quality of life.
- ii. Potential genetic markers include nitric oxide synthase polymorphisms, but others will be studied as relevant in searches of the scientific literature.
- iii. To investigate whether there is a difference in blood biomarkers between the two groups and whether biomarkers may be associated with outcome. Potential biomarkers include S-100 / nitric oxide (NOx) but others will be studied as relevant in searches of the scientific literature.

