**14 Table C.-Timing of outcome assessments**

Assessments	Screen	Day 0 Baseline Pre- treatment	Day 0 Post- treatment	Day 1 During treatment	Day 2 After treatment	Discharge, Death	Day 90 Telephone
Face-to-face							
Clinical assessment	X 				X	X	
Eligibility screening	X						
CT Scan		X 	or X 				
Consent		X		or X	or X		
Randomisation		X					
GTN/Sham patch			X	X			
mRS		X 					
U & E FBC		X 					
Blood pressure		X 	X	X			
NIHSS		X 			X		
DSRS		X			X		
Blood biomarkers		X 			X 		

Hospital utilisation						X 	
Listed events				X 	X 		
SAEs, non-fatal			X	X	X		
SAEs fatal				X	X	X	X 
mRS							X 
Barthel Index							X 
EuroQoL							X 
Cognition (t-MMSE, TICS)							X 
Mood (ZDS)							X 

CT: Computerised tomography

NIHSS: National Institutes of Health stroke scale

MMSE: Mini-Mental State Examination

mRS modified Rankin scale

SAEs: Serious Adverse Events

1. Routine as part of clinical practice

2. Pre-morbid mRS

3. Biomarkers: soluble markers, genetics

4. Open-label blood pressure lowering, intravenous thrombolysis, mechanical thrombectomy, hyperacute stroke unit, Stroke Rehabilitation Unit, physiotherapy, occupational therapy, speech & language therapy, surgery for IS – hemicraniectomy, surgery for ICH, days in intensive/critical care unit.

5. Hypotension, hypertension, headache, infection

6. mRS [0 to 5, death=6], NIHSS [0 to 42, death=43], DSRS [0 to 12, death=13], GCS [3 to 15, death=2], BI [0 to 100, death=-5], EQ-5D [-0.5 to 1.0, death=0], EQ-VAS [0 to 100, death=-1], t-MMSE [0 to 22, death=-1], TICS-m [0 to 39, death=-1] and ZDS [ $\geq 70$ , death=102.5].

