**Table 3. Clinical Outcomes at Day 90.**

Data are number (%), median [interquartile range] or mean (standard deviation). Analyses performed using binary logistic regression (BLR), ordinal logistic regression (OLR) or multiple linear regression (MLR) with adjustment for age, time from stroke onset to randomisation, systolic blood pressure, stroke severity (NIHSS), and received reperfusion therapy. Mean (SD) and MLR will be used instead of median [IQR] and OLR for ordinal scales with more than 7 levels (central limit theorem/large sample). Cox proportional hazards regression (CPHR) will be used for death.

Variable	Statistic	N	All	GTN	Sham	aOR/aHR/aMD (95%CI)	Difference (p)
Patients randomised	N	xxx	xxx	xxx	xxx		
Outcomes							
Functional, modified Rankin scale (/6)							
	Median [IQR]	xxx	xxx [xxx]	xxx [xxx]	xxx [xxx]	xxx (xxx, xxx)	aOLR
	Mean (SD)	xxx	xxx [xxx]	xxx [xxx]	xxx [xxx]	xxx (xxx, xxx)	OLR aMLR
0	n(%)	xxx	xxx (xxx)	xxx (xxx)	xxx (xxx)		
1	n (%)	xxx	xxx (xxx)	xxx (xxx)	xxx (xxx)		
2	n (%)	xxx	xxx (xxx)	xxx (xxx)	xxx (xxx)		
3	n (%)	xxx	xxx (xxx)	xxx (xxx)	xxx (xxx)		
4	n (%)	xxx	xxx (xxx)	xxx (xxx)	xxx (xxx)		
5	n (%)	xxx	xxx (xxx)	xxx (xxx)	xxx (xxx)		
6	n (%)	xxx	xxx (xxx)	xxx (xxx)	xxx (xxx)		
Death	n (%)	xxx	xxx (xxx)	xxx (xxx)	xxx (xxx)	xxx (xxx, xxx)	CPHR
Disability							
Barthel index, BI (/100)	Mean (SD)	xxx	xxx (xxx)	xxx (xxx)	xxx (xxx)	xxx (xxx, xxx)	MLR
Cognition							
Telephone, MMSE (/22)	Mean (SD)	xxx	xxx (xxx)	xxx (xxx)	xxx (xxx)	xxx (xxx, xxx)	MLR
TICS-M (/39)	Mean (SD)	xxx	xxx (xxx)	xxx (xxx)	xxx (xxx)	xxx (xxx, xxx)	MLR
Animal naming	Mean (SD)	xxx	xxx (xxx)	xxx (xxx)	xxx (xxx)	xxx (xxx, xxx)	MLR
Mood							
Zung depression scale, ZDS(/102.5)	Mean (SD)	xxx	xxx (xxx)	xxx (xxx)	xxx (xxx)	xxx (xxx, xxx)	MLR

Variable	Statistic	N	All	GTN	Sham	aOR/aHR/aMD (95%CI)	Difference (p)
Quality of Life							
EQ-5D HSUV (/1)	Mean (SD)	xxx	xxx (xxx)	xxx (xxx)	xxx (xxx)	xxx (xxx, xxx)	OLR
EQ-VAS (/100)	Mean (SD)	xxx	xxx (xxx)	xxx (xxx)	xxx (xxx)	xxx (xxx, xxx)	OLR
Disposition						xxx (xxx, xxx)	OLR
...Home	n (%)	xxx	xxx (xxx)	xxx (xxx)	xxx (xxx)		
...Institution/in hospital	n (%)	xxx	xxx (xxx)	xxx (xxx)	xxx (xxx)		
...Died	n (%)	xxx	xxx (xxx)	xxx (xxx)	xxx (xxx)		
Events							
Recurrent Stroke	n (%)	xxx	xxx (xxx)	xxx (xxx)	xxx (xxx)	xxx (xxx, xxx)	BLR

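### The day-90 scales are compared only with deaths scored in, so the plan cannot tell an effect on mood, cognition, quality of life or disability from an effect on death

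*SAP*

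**What the plan says.** Objective 7b(i) of the SAP is "To identify potential proof of concept on whether GTN reduces disability, low mood, poor cognition, and low quality of life". The scales that serve it are listed in SAP 24b under day 90.

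Footnote 6 to Table C in SAP section 14 gives each scale a value for death: "BI [0 to 100, death=-5], EQ-5D [-0.5 to 1.0, death=0], EQ-VAS [0 to 100, death=-1], t-MMSE [0 to 22, death=-1" and "TICS-m [0 to 39, death=-1", with 102.5 for Zung. The value for animal naming, -1, appears only in Protocol Appendix G. The footnote to SAP Table 3 repeats most of these scores under the day-90 results, but prints 5 for Barthel and omits t-MMSE and animal naming.

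For the comparison, SAP 25c assigns "multiple linear regression (BI, TICS, t-MMSE, ZDS, EQ-5D, EQ-VAS, as appropriate". The Table 3 header agrees: "Mean (SD) and MLR will be used instead of median [IQR] and OLR for ordinal scales with more than 7 levels". The rows for EQ-5D HSUV and EQ-VAS in the same table are nevertheless labelled OLR.

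Death also has its own row ("Cox proportional hazards regression (CPHR) will be used for death") and is level 6 of the mRS. SAP 25g plans sensitivity analyses for the mRS alone. Table 3 has no survivor column or row.

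**The concern.** A regression on a scale that includes scored deaths compares a mixture of who died and how the survivors scored. The hypothesis tested is that this mixture is the same in both arms. Objective 7b(i) asks about the domains themselves, and nothing planned for these scales separates the two parts.

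This can mislead in two directions. A difference in deaths alone can show up on several rows at once and be read as separate signals for mood, cognition and quality of life. A real effect on one domain, with equal deaths, can be hidden by the variance that the death scores add.

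The SAP background shows how such a reading arises. It says of the early-treated subgroup of ENOS (ENOS-early) that "treatment with GTN was associated with reduced death, and improved functional outcome (mRS, BI) and quality of life", where deaths were 8% against 20%.

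**Working it through.** **Inputs.**
- SAP Table B, ENOS-early, GTN against no GTN: EQ-VAS 62 (29) against 53 (35); Barthel 74 (34) against 60 (41); deaths 11 (8%) against 26 (20%).
- SAP Table B, RIGHT-2: deaths 23% against 19%.
- Death scores: EQ-VAS -1 and Barthel -5 (SAP section 14).
- Planned size: 50 + 10 = 60 per arm (SAP section 9).

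The plan gives no power figure for these scales. Its only one (SAP section 9) concerns the mRS and is not used here.

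**Check of the inputs.** The implied group sizes are 11/0.08 ≈ 138 and 26/0.20 = 130. The unadjusted standard error for Barthel is √(34²/138 + 41²/130) = 4.62, which gives 14 (5.0 to 23.0). The printed result is 14 (4.6 to 22.5), so the table is coherent.

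**Step 1: survivor means in ENOS-early.** Assume that trial used the same death scores. With overall mean m, death proportion p and death score d, the survivor mean is (m - p·d)/(1 - p).
- EQ-VAS: (62 + 0.08)/0.92 = 67.5 and (53 + 0.20)/0.80 = 66.5, a difference of 1.0 out of 9.
- Barthel: (74 + 0.40)/0.92 = 80.9 and (60 + 1.0)/0.80 = 76.25, a difference of 4.6 out of 14.

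The implied survivor SDs are 23.2 and 24.9 for EQ-VAS, and 25.8 and 27.9 for Barthel. These are plausible and do not contradict the assumption. Allowing for rounding of both the percentages and the means, the survivor difference is -1.0 to 2.9 for EQ-VAS and 2.5 to 6.8 for Barthel.

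**Step 2: only deaths differ.** Simulation with 60 per arm, survivor EQ-VAS drawn with mean 67 and SD 24, clipped to 0-100, and an unadjusted two-sided t-test at 5%:

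| Deaths | Death-scored test significant | Survivors only |
|---|---|---|
| 8% vs 20% | 29% | 5% |
| 23% vs 19% | 7% | 5% |

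With a different survivor distribution and 50-60 per arm, the first row becomes 23-29% across EQ-VAS and Barthel. With a rank test, as a rough stand-in for ordinal regression, it is about 20%.

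**Step 3: true survivor effect, equal deaths.** Same setting, with a nominal 12-point benefit (about 10.4 points after clipping):

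| Deaths in both arms | Death-scored | Survivors only | Relative loss |
|---|---|---|---|
| 8% | 46% | 72% | 36% |
| 14% | 33% | 68% | 51% |
| 20% | 26% | 66% | 61% |

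With survivor means of 67 against 55, where clipping matters less, the death-scored power is 53/41/33% against 73/72/66% in survivors, a loss of 27/43/50%. With the rank test in the first setting, the death-scored power is 59/49/39%.

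**Step 4: why, in a formula.** With equal deaths p, survivor SD s and distance D from survivor mean to death score, scoring the deaths multiplies the non-centrality by 1/√(1 + p(D/s)²). For EQ-VAS at p = 0.20, D = 67.5 and s = 24.9, the factor is 0.636, which turns 80% power into 43%. At p = 0.08, D = 68.5 and s = 23.2, it is 0.768, which turns 80% into 58%. For Barthel the corresponding figures are 40% and 53%.

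For EQ-5D, death is 0 on a range of -0.5 to 1.0, so D is smaller relative to the scale. Assuming a survivor mean of 0.5-0.7 and SD of 0.25-0.30 (not in the documents), 80% falls to 59-72% at 8% deaths and to 42-61% at 20%.

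**Step 5: the Barthel footnote.** A death score of 5, as printed under Table 3, would place a dead participant above a survivor scoring 0. It would also change step 1 to (74 - 0.4)/0.92 = 80.0 and (60 - 1.0)/0.80 = 73.75, a difference of 6.25 instead of 4.6.

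**The case against.** Scoring death is a defensible choice. It keeps every randomised participant with a known outcome, in line with the intention-to-treat population in SAP section 18. A survivor comparison conditions on something that happens after randomisation. Table 3 shows deaths by arm and lists most of the death scores, so a careful reader can see the composite. The comparisons are labelled exploratory, and the Protocol (Assessment of efficacy) plans no formal efficacy assessment. All of this stands, and it is why the death-scored analysis should stay.

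Several stronger readings are tempting, but the documents do not support them.
- *The 29% is a false-positive rate.* The hypothesis tested includes death, and at 8% against 20% it is false. The error lies in attributing the result to a domain. The figure also uses the largest mortality gap in the documents.
- *The scales are tested only by linear regression, with death always at the extreme.* Table 3 says OLR for two scales, and the EQ-5D death score lies inside its range.
- *Half the power is always lost.* At 8% deaths the loss is nearer one third. The simulation also ignores the covariate adjustment in SAP 25d.
- *The ENOS-early quality-of-life result was only mortality.* This needs a scoring rule and EQ-VAS denominators that the documents do not print. On the same assumption, part of the Barthel difference remains among survivors.
- *A misread signal would drive the definitive trial.* Progression rests on recruitment, compliance and follow-up (SAP 25b), and the proposed definitive outcome is death or dependency on the mRS.

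A rule that reports a domain signal only when the survivor difference has the same sign also looks attractive, but it would do little. When only deaths differ, the survivor difference points the same way in 83% of the significant trials, so the rule cuts 29% only to about 0.29 × 0.83 = 24%. It would also let a non-randomised comparison veto a randomised one.

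**Conclusion.** The point holds as a gap in interpretation. As written, objective 7b(i) is answered only through a composite of death and scale, and no planned output shows how much of a difference lies among survivors.

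The size depends on mortality. When only deaths differ, a significant result occurs in about 29% of trials at the widest gap in the documents and about 7% at the RIGHT-2 rates. With equal deaths, power falls by about one third at 8% mortality and by roughly half or more at 14-20%, with smaller losses for EQ-5D and for a rank or ordinal analysis. These figures assume 60 per arm, EQ-VAS-like survivor scores and no covariate adjustment.

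If ENOS-early used the same scores, about 1 of its 9 EQ-VAS points and about 5 of its 14 Barthel points lie among survivors, within the wider ranges given in the working. Nothing here affects the feasibility endpoint. This is a cheap improvement, best made before database lock.

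**What to change.** In SAP 25c and Table 3:
- Keep the death-scored analysis and label the rows for Barthel, t-MMSE, TICS-M, animal naming, Zung, EQ-5D HSUV and EQ-VAS as *including death*.
- Beside each, add survivor n, mean (SD) and the adjusted difference with 95% CI, marked as descriptive and not protected by randomisation.
- State that results under 7b(i) are read from the composite, the survivor summary and the death row together. Do not add a rule that depends on the sign of the survivor difference.
- Reconcile the Barthel death score: 5 under Table 3, against -5 in SAP section 14 and Protocol Appendix D.
- Add the t-MMSE and animal-naming death scores to the Table 3 footnote.
- Reconcile MLR (25c and the Table 3 header) with OLR (Table 3 rows) for EQ-5D and EQ-VAS.

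The cost is a few lines of SAP text and extra columns, with no new data. The downside is a survivor comparison that conditions on a post-randomisation event and could itself be over-read, which is why it needs its label.
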